#### 4.7. PHARMACODYNAMIC ANALYSIS SET [PDS]

The PD analysis set will include all patients who receive both planned doses of SAIT101 or MabThera® or Rituxan® in Part A (i.e., first course), have at least one measured CD19+ count at scheduled time point postdose and have no major protocol deviations or events thought to significantly affect the PD of the drug.

Subjects in the PDS will be analyzed according to the treatment received.

#### 4.8. PROTOCOL DEVIATIONS

Criteria defining protocol deviations are referenced in the Protocol Deviation Guidance and Protocol Deviation Specification. Protocol Deviation specification will be developed according to the guidance and updated whenever new version of the guidance is released. Additional update before unblinding may be added in case of the protocol deviations are not specified in the guidance but are reported from sites and classified critical/major.

All Critical/Major protocol deviations captured by programming or reported protocol deviations from sites, which will be transferred to the biostatistics (BIOS) group by project manager in IQVIA via email, will be summarized by category of deviation (e.g. Inclusion criteria) and treatment group using the RAN; and all protocol deviations will be listed.

Protocol deviations do not lead to subject withdrawal unless they indicate a significant risk to the subject's safety. Protocol deviations leading to subject exclusion from the specific analysis set (except for PK set and PD set) will be pre-defined at Protocol Deviation Specification and get approval prior to database lock.

---

Document:	\\ieedc-vnasc01\Biosdata\Archigen\SAIT101\YWA21301\Biostatistics\Documentation\SAP	Version Number:	V2.0
Author:		Version Date:	13Feb2019

Template No: CS\_TP\_BS016 Revision 4  
Effective Date: 01Apr2016

Reference: CS\_WI\_BS005

#### 4.8.1. DEVIATIONS RELATED TO PHARMACOKINETIC AND PHARMACODYNAMIC ANALYSIS

Changes to the procedures or events, which impact the quality of the PK and PD data, will be considered significant protocol deviations and will be described within the CSR body text. These changes or events will include any circumstances that will alter the evaluation of the PK and PD.

Examples of protocol deviations that are important for PK and actions to be taken are discussed in Section 13.

In the case of a significant protocol deviation or event, PK and PD data collected during the affected treatment period will be excluded from summaries and analyses but included in by-subject listings. Other changes to the procedures or events which do not impact the quality of the PK data will not be considered significant protocol deviations. In general, a common example of a non-significant protocol deviation is deviations from blood sample collection times.

## 5. General Considerations

All patients will be tabulated according to their initial treatment group for analyses when all study team are blinded; while for final analysis (W52 CSR), both initial first and second courses of study treatment group will be considered, regardless of any dose adjustment during study conduct.

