### 6.2 Statistical Methods

Categorical variables will be summarized by the number and percentage of patients in each category. Continuous variables will be summarized using N, mean, standard deviation (SD), median, minimum, and maximum values.

For all efficacy analyses, patients will be analyzed under the treatment they were randomized to, even if the treatment actually received differs from the treatment the patient was randomized to receive. For all safety analyses, patients will be analyzed under the treatment they actually received.

Generally, the Baseline value to be used in any change from Baseline listings/summaries/graphical presentations or as a covariate in a statistical analysis is defined as the latest available pre-randomization value. If necessary, detailed Baseline definitions of specific parameters or assessments will be defined in the statistical analysis plan (SAP).

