### **6.9 Interim Analysis**

Interim analysis of 10 patients per group (30 patients in total) of safety data collected up to Week 4 and 20 patients per group (60 patients in total) of safety data collected up to Week 12 are planned. Safety data will be handled by unblinded study team in CRO for interim analysis, and the safety report will be submitted to regulatory. The study will be unblinded at Week 24 and an interim CSR will be prepared based on the 24-week data of all patients. The investigators and patients will remain blinded to treatment assignment during the post Week 24 follow-up period.

After review by DSMB, this analysis will be reported to health authorities upon request.

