## 1. Introduction

This document describes the rules and conventions to be used in the presentation and analysis of pharmacokinetics (PK), efficacy, safety, pharmacodynamics (PD), and immunogenicity data for Protocol AGB001. It describes the data to be summarized and analyzed, including specifics of the statistical analyses to be performed. The following analyses will be performed for this study analysis for third data and safety monitoring board (DSMB) analysis and additional if needed, analysis for period till Week 52 (Week 52 CSR).

This statistical analysis plan (SAP) is based on protocol version amendment 04, dated 27Apr2017.

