### 2.4. RANDOMIZATION

In Part A, patients will be randomized in a 1:1:1 ratio to receive the first course of SAIT101 (n=94) versus Rituxan® (n=94) versus MabThera® (n=94). The first course includes two intravenous (i.v.) 1,000 mg study drug infusions: one on Day 1 (Visit 2) and the second on Day 15 (Visit 5).

Document: \\ieedc-vnasc01\Biosdata\Archigen\SAIT101\YWA21301\Biostatistics\Documentation\SAP  
 Author: Version Number: V2.0  
 Version Date: 13Feb2019

Template No: CS\_TP\_BS016 Revision 4 Reference: CS\_WI\_BS005  
 Effective Date: 01Apr2016

In Part B, eligible patients in the SAIT101 arm or MabThera® arm will receive the second course of SAIT101 treatment or MabThera®, respectively, at Week 24 and Week 26, however, in the Rituxan® arm will be randomized in a 1:1 ratio to receive SAIT101 or Rituxan® treatment at Weeks 24 and 26. The second course includes two 1,000 mg i.v. infusions (one at Week 24 and the second infusion at Week 26 [14 days later]) of study drug.

At Week 24, patients will be evaluated for further course of the infusion, i.e. Part B.

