### 3.1. DATA AND SAFETY MONITORING BOARD (DSMB)

There will be at least 3 DSMB meetings for reviewing safety data in this study. Analysis for first and second DSMB meetings will be described in a separate DSMB SAP; while the third (all patients at week 26) and onward will be based on this SAP where analyses described in section 8-12 and 16 will be performed. Other analyses may be added in case they are thought to affect DSMB safety review, however no statistical inference will be included in order to avoid an inflation of the type I error.

The first DSMB analysis will be considered as Interim Analysis of 10 patients per group (30 patients in total) of safety data collected up to Week 4 whose safety report will be submitted to regulatory. For additional details on DSMB meetings, please refer to the DSMB charter dated 26Jan2017.

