### 3.2. FINAL ANALYSIS (W52 CSR)

The analysis of primary, secondary and exploratory endpoints, including PK/PD, efficacy, safety and

---

Document:	\\eedc-vnasc01\Biosdata\Archigen\SAIT101\YWA21301\Biostatistics\Documentation\SAP		
Author:		Version Number:	V2.0
		Version Date:	13Feb2019

Template No: CS\_TP\_BS016 Revision 4  
Effective Date: 01Apr2016

Reference: CS\_WI\_BS005

immunogenicity, will be performed per protocol based on procedures outlined in this SAP based on the 52-week data of all patients.

The study will be unblinded only at Week 52 and a Week 52 CSR (W52 CSR) will be prepared based on the 52-week data of all patients.

The analysis for W52 CSR will be performed by IQVIA Biostatistics following sponsor authorization of this Statistical Analysis Plan, database lock and sponsor authorization of analysis sets.

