### **4.4. SAFETY ANALYSIS SET [SAF]**

The Safety Analysis Set (SAF) consists of all RAN patients who received at least one dose of study drug during Part A or Part B. Subjects will be analyzed according to the treatment received. The SAF is used as the basis for all safety analyses up to Week 52.

---

Document:	\\ieedc-vnasc01\Biosdata\Archigen\SAIT101\YWA21301\Biostatistics\Documentation\SAP	Version Number:	V2.0
Author:		Version Date:	13Feb2019

Template No: CS\_TP\_BS016 Revision 4  
Effective Date: 01Apr2016

Reference: CS\_WI\_BS005

If there is any doubt whether a subject was treated or not, they will be assumed treated for the purposes of analysis.

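### DSMB 3 safety tables: read naturally, SAP 5 counts second-course SAIT101 doses and events in switched Rituxan patients under Rituxan

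*SAP*

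**What the plan says.** SAP 5 sets the grouping rule: "All patients will be tabulated according to their initial treatment group for analyses when all study team are blinded". The rest of that sentence says that the Week 52 report will consider the first and second courses, without saying how.

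SAP 3 plans two kinds of analysis: DSMB reviews and the final analysis.
- **DSMB reviews.** The first two have their own SAP; "the third (all patients at week 26) and onward will be based on this SAP", using Sections 8 to 12 and 16. SAP 1 likewise lists the "third data and safety monitoring board (DSMB) analysis and additional if needed".
- **Unblinding.** SAP 3.2 states "The study will be unblinded only at Week 52".
- **Part B.** Under SAP 2.4, eligible patients "in the Rituxan® arm will be randomized in a 1:1 ratio to receive SAIT101 or Rituxan® treatment at Weeks 24 and 26". The SAIT101 and MabThera arms keep their own product.

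For safety, protocol 6.2 says "For all safety analyses, patients will be analyzed under the treatment they actually received". SAP 4.4 defines the Safety Analysis Set over Parts A and B and says "Subjects will be analyzed according to the treatment received". SAP 16.1 anchors treatment-emergent events to the first dose of study drug, with no attribution by course. SAP 17 does separate four sequences, including Rituxan then SAIT101, but only for immunogenicity, and Section 17 is not among those listed for DSMB 3.

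**The concern.** The switch from Rituxan to SAIT101 is the new exposure in Part B, and DSMB 3 is the first review under this SAP that includes it. Under initial-group columns, a reaction to SAIT101 given at Week 24 to a switched patient raises the Rituxan rate and leaves the SAIT101 rate unchanged. The exposure tables in SAP 12.1 would likewise show those SAIT101 infusions as Rituxan. No summary column would isolate the switched patients.

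A second feature works in the same direction. SAP 16.1 counts a patient once per preferred term, and protocol 5.4.5 fixes the reported term for infusion reactions. A switched patient who already reacted in Part A and reacts again to SAIT101 adds nothing to the overall incidence table. The repeat could still show in the severity (worst case), serious or drug-interruption tables.

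**Working it through.** The plan states no figure on this point, so the check is first textual, then a sizing under stated assumptions.

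**Text**
1. SAP 5 has two branches: initial group while the study team is blinded, and both courses for the Week 52 report.
2. DSMB 3 is at Week 26 and unblinding is at Week 52, so of the two branches DSMB 3 falls in the first.
3. The first Part B infusion is at Week 24, so DSMB 3 data include it.
4. The treatment-received rule points the other way for switched patients. In protocol 6.2 it follows the contrasting efficacy rule for patients whose treatment received differs from that randomized. That context suggests misallocated drug, not a planned switch, and the text gives no tie-break.

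**Number switched**
Inputs: 94 Rituxan patients (SAP 2.3) and 1:1 re-randomization (SAP 2.4). Assumptions: all 94 are dosed and reach Week 26; 30%, 50% or 70% are retreated (the documents give no share); 10% of switched patients react; the data cut is per patient at Week 26.

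Switched = 94 × share × 0.5. Patients with a reaction = switched × 0.10. Points added to the Rituxan column = reactions / 94.

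| Retreated (assumed) | Switched | Share of Rituxan column | Patients with a reaction | Points added to Rituxan |
|---|---|---|---|---|
| 30% | 14.1 | 15% | 1.41 | 1.5 |
| 50% | 23.5 | 25% | 2.35 | 2.5 |
| 70% | 32.9 | 35% | 3.29 | 3.5 |

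The SAIT101 column gains nothing from these events. If 20% of those who react had the same preferred term in Part A (assumed), the added points fall by a factor of 0.8, to 1.2, 2.0 and 2.8.

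**A result that does not depend on the retreated share**
Let the share e be equal across arms. Second-course SAIT101 recipients number 94e + 47e = 141e, of whom 47e sit under Rituxan: one third. If second-course risk depends only on the product then given (p1 for SAIT101, p0 for Rituxan), the tabulated difference among retreated patients is p1 − (p0 + p1)/2 = (p1 − p0)/2. A true 20% versus 10% would show as 5 points instead of 10.

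**Exposure time**
The visit windows are Day 169 ± 3 and Day 183 ± 3. Time from switch to Week 26 runs from (183 − 3) − (169 + 3) = 8 days to (183 + 3) − (169 − 3) = 20 days, nominally 14. At 2 weeks each, switched patients contribute 28.2, 47.0 or 65.8 patient-weeks out of 94 × 26 = 2,444, or 1.2%, 1.9% or 2.7%. Late events are therefore barely affected at DSMB 3. Acute reactions are affected, because protocol 5.4.5 says they generally occur within 24 hours of infusion.

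**The case against.** The strongest reply is that SAP 5 may not govern DSMB output at all. Its condition is that the whole study team is blinded. Protocol 3.5.4 unblinds DSMB members, and protocol 6.9 says "Safety data will be handled by unblinded study team in CRO for interim analysis". Initial-group columns also make sense for blinded deliveries: only the Rituxan arm splits at Week 24, so four sequence columns would identify that arm even under masked labels. This lowers certainty. However, protocol 6.9 ties the unblinded team to the 10- and 20-per-group analyses and does not name DSMB 3. If DSMB 3 falls outside the blinded branch, it falls in neither branch of SAP 5, leaving only a treatment-received rule that does not address switched patients.

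The table templates (SAP 7) and the DSMB charter (SAP 3.1) may fix the columns, and neither is available. That stands, so the actual layout cannot be known from these documents.

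The DSMB would also not be blind to the events. SAP 16.1 lists all adverse events and gives infusion reactions of special interest their own summary, SAP 12.1 lists dosing, and protocol 5.4 puts events of special interest on expedited timelines. A post-switch reaction can be traced patient by patient. This limits the harm but does not supply a rate for switched patients.

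A reader might infer that no rule anywhere places a patient given two products. The documents do not support that: SAP 5 considers both courses at Week 52, and SAP 17 names a Rituxan–SAIT101 group.

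**Conclusion.** The point holds, confined to DSMB safety and exposure summaries at DSMB 3 and any later review before unblinding. On its natural reading, SAP 5 places second-course SAIT101 data from switched patients under Rituxan, in conflict with protocol 6.2 and SAP 4.4. Confidence is medium because of the blinding condition and the two unseen documents.

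The size is modest: about 1 to 3 patients, or 1.5 to 3.5 percentage points in the Rituxan column. This rests on the assumed retreatment and reaction rates, full follow-up of 94 patients and a per-patient Week 26 cut. A later cut, or a later DSMB review, would bring in more post-switch time.

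It would be tempting to conclude that the final safety comparison or the equivalence conclusions are biased. The documents do not support that: DSMB tables carry no inference (SAP 3.1), and the primary and main efficacy endpoints are not involved. It is a correction worth making before DSMB tables are run, not a threat to the trial's result.

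**What to change.** In SAP 5, limit initial-group tabulation to data before the first Part B infusion. For DSMB 3 onward, have the unblinded team tabulate Part B exposure and adverse events with onset on or after the start of that infusion, for the DSMB only:
- by the four SAP 17 sequences (SAIT101–SAIT101, MabThera–MabThera, Rituxan–Rituxan, Rituxan–SAIT101);
- with patients infused in Part B as the denominator;
- with each patient counted once per preferred term within Part B.

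If the templates or charter already do this, a cross-reference in SAP 5 is enough.

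The cost is one sentence and one extra set of DSMB tables. SAP 3.1 already allows added analyses for DSMB safety review. Site and sponsor blinding, the endpoints and the Week 52 analysis are unchanged.

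The drawback is imprecision. With zero events among n switched patients, the exact 95% upper limit is 1 − 0.025^(1/n): 23%, 14% and 11% for n = 14, 24 and 33. The new columns would show where reactions fall but could not rule out a raised rate.

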### 5.1. STUDY DAY

Study Day in days will be calculated from the date first study drug administration date and it will be used to show start/stop day of assessment or event. Study Day of the first study drug date will be Day 1.

If the date of the event is on or after the first study drug date then:

- Study Day = date of event – first study drug date + 1.

If the date of the event is prior to the first study drug date, then:

- Study Day = date of event – first study drug date.

In the situation where the event date is partial or missing, the date will appear partial or missing in the listings and Study Day will be calculated after proper imputation has been carried out as described in [Appendix 1](#).

### 5.2. BASELINE

Unless otherwise specified, baseline is defined as the last non-missing measurement taken prior to first study drug date after informed consent is obtained (including unscheduled assessments). In the case where the last non-missing measurement and the reference start date coincide, that measurement will be considered pre-reference, but AEs and medications commencing on the reference start date will be considered post-reference. For vital sign, joint assessments, patient's global assessments, physician's global assessments, CRP and ESR, both date and time will be considered for defining baseline.

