- t On Day 1, Day 15 (Week 2), and Week 24: immunogenicity sample will be collected before start of infusion. Wherever possible immunogenicity blood samples will be taken at the same time as blood is drawn for other analyses to limit repeated venipuncture. Immunogenicity sampling is also taken when patients show signs or symptoms of immune-response-related adverse events.

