### **3.6.4 Immunogenicity Assessments**

Blood samples (approximately 5 to 8 mL) will be taken at the visits shown in (Table 2) to determine the incidence of HACA and neutralizing antibody (using validated analytical methods).

Blood immunogenicity samples will be collected on Day 1 of First course (prior to the start of the first infusion), and on Weeks 1, 2, 4, 12, 16, 24, 36, and 52 with date and time of sampling accurately recorded. Wherever possible immunogenicity blood samples will be taken at the same time as blood is drawn for other analyses to limit repeated venipuncture. Additionally, immunogenicity should be assessed when patients show signs or symptoms of immune-response-related adverse events.

Human anti-chimeric antibody will be detected in serum samples using validated analytical methods. Serum samples in which HACA are detected will be reflexed to a Neutralizing Antibody Assay to evaluate the effect of the HACA on the biological activity of rituximab. Full instructions for collection, labeling, storage, and shipment of samples are provided in the Laboratory Manual.

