#### **5.4.5 Infusion Reactions**

An acute onset infusion reaction generally occurs within 24 hours of infusion of the study drug. Rituximab can cause severe, including fatal, infusion reactions. Severe reactions typically occur during the first infusion with time to onset of 30 to 120 minutes. Rituximab-induced infusion reactions and sequelae include urticaria, hypotension, angioedema, hypoxia, bronchospasm, pulmonary infiltrates, acute respiratory distress syndrome,

myocardial infarction, ventricular fibrillation, cardiogenic shock, anaphylactoid events, or death.

Medical management (e.g., glucocorticoids, epinephrine, bronchodilators, or oxygen) for infusion reactions must be instituted as needed. Depending on the severity of the infusion reaction and the required interventions, rituximab may be temporarily or permanently discontinued. Resume infusion at a minimum 50% reduction in rate after symptoms have resolved. Closely monitor patients with pre-existing cardiac or pulmonary conditions.

Infusion reactions should be reported in the eCRF as AEs, or SAEs if it meets the seriousness criteria, with the event term “infusion-related reaction”. The signs and symptoms of the infusion reaction should be described in the appropriate part of the eCRF. Please refer also to Section 5.4.6 (Anaphylaxis).

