test (SAIT101) and the reference (MabThera® or Rituxan®) treatments and the associated 90% CI will be calculated. Comparison between the reference treatments will also be performed. Back transformation will provide the ratio of geometric means between treatments and 90% CI for this ratio. Equivalence will be concluded if the 90% CI for the ratio of geometric means of test/reference for primary endpoints are completely contained within the acceptance interval of 0.80 to 1.25. Least-squares geometric means will be also presented for each treatment with corresponding 95% CIs. BLQ values for  $C_{trough}$  will be treated as LOQ/2 for all statistical comparison. Line plots will be generated to visually display all comparisons for all primary parameters.

A sensitivity analysis will be performed for the above comparisons, in which the above comparison will be replicated, with the addition of the following covariates to the statistical model: Age, sex, ADA status at baseline, body weight at baseline.

An exploratory statistical assessment of the impact of baseline ADA status (Positive or Negative) will be completed by adding this fixed effect to the model used in the primary statistical analysis. The ratio of geometric means for ADA positive/ADA negative will be reported with the 90% CI for this ratio.

Scatter plots of individual and geometric mean PK parameters  $AUC_{(0-inf)}$ ,  $AUC_{(0-t)}$ ,  $AUC_{(0-d15)}$ ,  $C_{max,dose2}$  after the second infusion on Day 15 and  $C_{trough}$  before the second infusion on Day 15 versus treatment will be presented. Additional, graphical presentations of PK data may be added at the discretion of the PK scientist, if further illustration of the PK results is deemed appropriate.

Additional impact analyses will be performed to evaluate the impact of site 10703 on the primary analysis, and the statistical significance of any PK differences associated with this site. The first impact analysis will entail repeating the primary analysis above but excluding site 10703. The second impact analysis will entail adding two fixed effects to the primary model: Site1073 (Yes/No), Site10703 x Treatment interaction, and testing both effects at the two-sided 5% significance level. The type 3 p-values will be reported for all effects in this model, but no treatment or site comparison estimates will be made.

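### SAP 5.2 can admit a Day 1 sample drawn after dosing as baseline for antibody status and safety laboratories, because clock time is checked only for other assessments

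*SAP*

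**What the plan says.** SAP 5.2 has three parts that matter here.

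- The default: "baseline is defined as the last non-missing measurement taken prior to first study drug date after informed consent is obtained (including unscheduled assessments".
- The same-day clause: "In the case where the last non-missing measurement and the reference start date coincide, that measurement will be considered pre-reference". In the same sentence, adverse events and medications that start on that day are counted as post-reference.
- The exception: for vital signs, joint assessments, the patient and physician global assessments, CRP and ESR, "both date and time will be considered for defining baseline". HACA/ADA, hematology, other chemistry and urinalysis are not on this list.

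Some variables have their own baseline. SAP 14.1 ties CD19+ counts to the value immediately before the first infusion and immunoglobulins to screening. ADA status at baseline has no such definition. SAP 17 names Day 1 predose only as a visit at which HACA incidence is summarized.

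Protocol 6.2 sets the general baseline as the latest value before randomization and leaves parameter-specific detail to the SAP. SAP 2.6, which lists changes from the protocol, does not mention baseline.

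On sampling, Protocol Table 2 footnote t states: "Immunogenicity sampling is also taken when patients show signs or symptoms of immune-response-related adverse events". Protocol 3.6.4 repeats this and asks for the date and time of immunogenicity samples to be recorded. Table 2 footnote k leaves tests at unscheduled visits to the investigator. Protocol 5.4.5 says of infusion reactions: "Severe reactions typically occur during the first infusion with time to onset of 30 to 120 minutes".

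**The concern.** For the assessments not on the time-checked list, a sample is judged by its date. A sample drawn during or after the first infusion carries the first-dose date, so the same-day clause classes it as pre-reference, and the default rule counts it even if it was unscheduled. An event that starts during the infusion is post-dose under SAP 5.2, yet a sample drawn because of that event is pre-dose.

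Baseline ADA status is used in several places:

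- a covariate in the PK sensitivity model ("Age, sex, ADA status at baseline, body weight at baseline") and in the main-efficacy sensitivity model (SAP 15.1.4);
- the added fixed effect in the exploratory PK model, and a grouping for PK summaries (SAP 13.2);
- the grouping for the PK and PD plots (SAP 13.3, 14.3);
- an efficacy subgroup (SAP 15.2.4).

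If the value is post-exposure, these analyses adjust for or group by something measured after treatment began, and they do so in patients suspected of an immune reaction. For safety laboratories, SAP 16.2 measures change and shift from baseline. A value taken during an acute event would become the reference for every later visit.

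**Working it through.** The plan gives no figure to reproduce. The check is to apply SAP 5.2 to a constructed record for a parameter outside the time-checked list.

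Inputs:

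- a screening sample, negative;
- the scheduled Day 1 sample, 1 hour before dosing, negative (Protocol 3.6.1 places assessments before pre-medication; Table 2 footnote t places the Day 1 antibody sample before the infusion);
- an unscheduled Day 1 sample 90 minutes after the infusion starts, positive (a constructed case, placed within the 30 to 120 minutes of Protocol 5.4.5).

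| Reading of SAP 5.2 | Record chosen as baseline | Before dosing? |
|---|---|---|
| Date only, with the same-day clause, last record taken | Unscheduled sample at 90 minutes | No |
| Date and time, as for CRP and ESR | Scheduled Day 1 sample | Yes |
| Opening sentence alone (before the first-dose date) | Screening sample | Yes |

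One paragraph therefore supports three different baselines for one patient. Under Protocol 6.2 the third sample could not be chosen, because randomization precedes the infusion.

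Two details bear on the first row. With time ignored, the two Day 1 samples are tied, and SAP 5.2 gives no rule to break the tie. Taking the later one is the natural meaning of a last measurement. SAP 5.3 leans the same way, since it uses the latest available result for retests at the same visit, but that rule is written for by-visit summaries.

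Tracing where a wrong baseline could go:

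- Primary PK: the ANOVA has no covariates (SAP 13.2). Not affected.
- Main efficacy: DAS28-CRP is built from joint counts and CRP (SAP 15.1.1), all time-checked in SAP 5.2. Not affected.
- CD19+ and immunoglobulins: own baselines (SAP 14.1). Not affected.
- Baseline-ADA covariates, exploratory model, subgroup, summaries and plots: exposed.
- Hematology, chemistry other than CRP, and urinalysis change and shift tables: exposed. ESR, which SAP 16.2 groups with hematology, is protected.

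**The case against.** The strongest reply is that SAP 5.2 is ambiguous and does not positively select a post-dose sample. Its opening requires a value before the first-dose date, and same-day samples tie once time is ignored. Elsewhere the intention is clearly predose: Protocol 2.3.4, 6.7 and Table 2 footnote t, and SAP 17, all place the Day 1 HACA sample before dosing. This stands in part. It means a post-dose sample can become baseline, not that it must. It does not remove the problem, because those places describe the scheduled sample, while SAP 5.2 expressly brings unscheduled ones into the baseline derivation.

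The second reply concerns the trigger. A reader might infer from Protocol 5.4.5 and footnote t together that every infusion reaction produces a same-day antibody sample. The documents do not say so. The extra sample is for immune-response-related events and has no stated timing, the infusion-reaction instructions in Protocol 3.2.1 and 5.4.5 request no antibody sample, and SAP 16.1 identifies the two kinds of event by different eCRF questions. Post-reaction laboratory tests are discretionary. This reply stands, and the laboratory route is the weaker of the two.

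Third, a reader might infer that an acute laboratory abnormality would vanish from the report. It would not. SAP 16.2 lists all values with high and low flags. Under Protocol 5.7 a clinically significant change is an adverse event, and one starting on the first-dose day is treatment-emergent under SAP 16.1. Only the reference for change and shift is at risk.

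Fourth, a reader might argue that the full 1,000 mg in the circulation would distort the antibody assay. Protocol Table 1 gives only 25 mg by 30 minutes and 25 + 50 + 75 + 100 = 250 mg by 120 minutes, and no assay drug tolerance is stated. Nothing in the documents shows how a same-day result would differ from the predose one.

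**Conclusion.** The point holds as a gap in a derivation rule. For HACA/ADA and for safety-laboratory parameters other than CRP and ESR, SAP 5.2 as written can admit a post-dose Day 1 sample as baseline, contrary to its own opening sentence and to Protocol 6.2. It requires an extra same-day sample after the infusion starts and a program that takes the later of two same-day records.

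Only sensitivity, exploratory and descriptive outputs are exposed. The primary PK and main DAS28-CRP conclusions cannot change through this route.

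The number of patients cannot be derived. The documents give neither a rate of Day 1 immune-response-related events nor the share of such patients who would be sampled the same day. A reader might multiply assumed rates by the 282 planned patients, but the result would be assumption only, and the true count may be zero. The case for correcting the rule is that one text yields three baselines and that the correction is cheap.

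**What to change.** In SAP 5.2:

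1. Define baseline for every parameter as the last non-missing value before the date and time at which the first infusion starts, unless a section gives its own definition.
2. If a same-day sample has no time, accept only the scheduled Day 1 predose record or an earlier one.
3. State that ADA status at baseline is the Day 1 predose HACA result.
4. Remove the conflict between the opening sentence and the same-day clause, and record in SAP 2.6 how the definition relates to Protocol 6.2.

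The cost is a few sentences and one change to the baseline derivation, made before unblinding. No new data are needed for antibodies, since Protocol 3.6.4 already asks for sampling times. The documents do not say the same for safety laboratories, and the second item covers any that lack a time.
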